21.0 Vulnerable Populations

NA

22.0 Community-Based Participatory Research

NA

23.0 Sharing of Results with Subjects

Individual response data is shared with the participant as a part of their clinical care.

24.0 Setting

All treatment will be conducted on an outpatient basis at RPCI's Gastrointestinal Center within Roswell Park Cancer Institute. Roswell. Potential study participants will be identified and recruited from current GI Center patients and from community referral.

25.0 Provisions to Protect the Privacy Interests of Subjects

Any data, specimens, forms, reports, video recordings, and other records that leave the site will be identified only by a participant identification number (Participant ID, PID) to maintain confidentiality. All records will be kept in a limited access environment. All computer entry and networking programs will be done using PIDs only. Information will not be released without written authorization of the participant.

26.0 Resources Available

NA

27.0 Prior Approvals

NA

28.0 Compensation for Research-Related Injury

Please refer to the informed consent form (Section 13) related to this study:

29.0 Economic Burden to Subjects

The participant and /or their insurance company will be responsible for charges related to the administration of drugs used in this clinical research study and for charges for medications that may be needed to prevent or control side effects.

30.0 Consent Process

This study will not be initiated until the protocol and informed consent document(s) have been reviewed and approved by a properly constituted Institutional Review Board (IRB) or Independent Ethics Committee (IEC). Each participant (or legal guardian) shall read, understand, and sign an instrument of informed consent prior to performance of any study-specific procedure. It is the responsibility of the investigator to ensure that the participant is made aware of the investigational nature of the treatment and that informed consent is given.

The Investigator is responsible for the retention of the participant log and participant records; although personal information may be reviewed by authorized persons, that information will be treated as strictly confidential and will not be made publicly available. The investigator is also responsible for obtaining participant authorization to access medical records and other applicable study specific information according to Health Insurance Portability and Accountability Act regulations (where applicable).

This study will be conducted in compliance with all applicable laws and regulations of the state and/or country and institution where the participant is treated. The clinical trial should be conducted in accordance with the ethical principles embodied in the Belmont Report: Ethical Principles and Guidelines for the Protection of Human Subjects of Research, consistent with good clinical practice and the applicable regulatory requirements and according to the guidelines in this protocol, including attached appendices.

31.0 Process to Document Consent in Writing

The Investigator (or IRB specified designee) is responsible for obtaining written consent from each participant in accordance with GCP guidelines using the approved informed consent form, before any study specific procedures (including screening procedures) are performed. The informed consent form acknowledges all information that must be given to the participant according to applicable GCP guidelines, including the purpose and nature of the study, the expected efficacy and possible side effects of the treatment(s), and specifying that refusal to participate will not influence further options for therapy. Any additional information that is applicable to the study must also be included. Additional national or institutionally mandated requirements for informed consent must also be adhered to. The participant should also be made aware that by signing the consent form, processing of sensitive clinical trial data and transfer to other countries for further processing is allowed.

The Investigator shall provide a copy of the signed consent form to the participant and the signed original shall be maintained in the Investigator File. A copy of the signed consent form must be filed in the participant file. At any stage, the participant may withdraw from the study and such a decision will not affect any further treatment options.

32.0 Drugs or Devices

32.1 Pembrolizumab

Pembrolizumab is a humanized monoclonal antibody that blocks the interaction between PD-1 and its ligands, PD-L1 and PD-L2. Pembrolizumab is an IgG4 kappa immunoglobulin with an approximate molecular weight of 149 kDa.

Roswell Park Protocol No.: I 35316

32.1.1 Active Substance and Source:

Product Name & Potency	Dosage Form
Pembrolizumab 50 mg	Lyophilized Powder for Injection
Pembrolizumab 100 mg/ 4mL	Solution for Injection

Pembrolizumab for injection is a sterile, preservative-free, white-to off-white lyophilized powder in single-use vials. Each vial is reconstituted and diluted for intravenous infusion. Each 2 mL of reconstituted solution contains 50 mg of pembrolizumab and is formulated in L-histidine (3.1 mg), polysorbate 80 (0.4 mg), and sucrose (140 mg). May contain hydrochloric acid/sodium hydroxide-adjust pH to 5.5.

Pembrolizumab injection is a sterile, preservative-free, clear to slightly opalescent, colorless to slightly yellow solution that requires dilution for intravenous infusion. Each vial contains 100 mg of pembrolizumab in 4 mL of solution. Each 1 mL of solution contains 25 mg of pembrolizumab and is formulated in: L-histidine (1.55 mg), polysorbate 80 (0.2 mg), sucrose (70 mg), and Water for Injection, USP.

32.1.2 Drug Shipment:

Pembrolizumab will be provided by Merck & Co., Inc. and shipped to the participating site. The investigational drug will be labeled in accordance with regulatory requirements (Drug identity, i.e., name, strength) is included in the label.

The date of receipt and the amount of drug received will be documented. Drug shipment records will be retained by the investigational pharmacist or designee.

32.1.3 Preparation:

Refer to Pharmacy Manual.

32.1.4 Storage and Stability:

The Investigator or designee will be responsible for ensuring that the investigational product is securely maintained in a locked, limited-access facility, in accordance with the applicable regulatory requirements.

Drug storage temperature will be maintained and recorded, as applicable.

Pembrolizumab for injection (lyophilized powder): Store vials under refrigeration at 2°C to 8°C (36°F to 46°F).

Pembrolizumab injection (solution): Store vials under refrigeration at 2°C to 8°C (36°F to 46°F) in original carton to protect from light. Do not freeze. Do not shake.

Refer to Investigator's Brochure for additional details.

32.1.5 Handling and Disposal:

The Investigator or designee will be responsible for dispensing and accounting for all investigational drug provided by Merck & Co., Inc., exercising accepted medical and pharmaceutical practices. Study drugs must be handled as cytotoxic agents and appropriate

Roswell Park Protocol No.: I 35316

precautions taken per the institution's environmentally safe handling procedures. All investigational drugs will be dispensed in accordance with the Investigator's prescription or written order.

All products dispensed will be recorded on a product accountability record. Records of product lot numbers and dates received will be entered on a product accountability form. This record will be reviewed during periodic monitoring visits. It is the Investigator's responsibility to ensure that an accurate record of investigational drug issued and returned is maintained.

All unused and/or partially used investigational drug will be destroyed according to standard practices after properly accounting for the dispensing. Partially used vials of study drug will not be re-used for other participants.

Under no circumstances will the Investigator supply investigational drug to a third party or allow the investigational drug to be used in a manner other than as directed by this protocol.

32.1.6 Overdose:

For purposes of this trial, an overdose of pembrolizumab will be defined as any dose of 1,000 mg or greater (≥ 5 times the indicated dose). No specific information is available on the treatment of overdose of pembrolizumab.

In the event of overdose, the participant should be observed closely for signs of toxicity. Appropriate supportive treatment should be provided if clinically indicated.

32.2 Sorafenib

Sorafenib will not be provided for this study and will be paid for by the patient's insurance carrier as part of the standard-of-care treatment for unresectable hepatocellular carcinoma. The starting dose of sorafenib is at the discretion of the physician based on clinical assessment of the patient.

Roswell Park Protocol No.: I 35316

2. INFORMED CONSENT

- Informed consent must be obtained by the **site Investigator/designee** from any participants wishing to participate, **prior to any procedures or treatment**.
- An informed consent template is provided by Roswell Park and can be amended to reflect institutional requirements.
- All consent changes **must** be reviewed by Roswell Park CRS QA Network Office prior to submission to the site IRB.
- The informed consent must be IRB approved.
- Always check that the most up to date version of the IRB approved consent is being used.
- Within 5 business days, notify the Roswell Park CRS QA Network Office of all participant withdrawals or consent to limited study participation and appropriately document the discontinuation and the reason(s) why.

3. PARTICIPANT REGISTRATION

The participant completes the Gender, Race, and Ethnicity Form and this is placed in the study binder.

RPCI does not grant exceptions to eligibility criteria.

Phase 1 Protocol Registration Instructions

Contact the Roswell Park Network QA Coordinator to verify that a slot is available in the open cohort when a participant has been identified. **Do not have the participant sign consent prior to verifying an open slot.**

- After the participant signs consent, the Subject Screening and Enrollment Log must be faxed or emailed ([contact]) to the Roswell Park

Roswell Park Protocol No.: I 35316

QA Coordinator Monitor within 1 business day. The Roswell Park QA Coordinator/Monitor will confirm receipt of the Subject Screening and Enrollment Log and email the participant ID number.

- When the participant has met eligibility, a signed eligibility checklist and other requested documentation will be faxed or emailed to the Roswell Park Network QA Coordinator.
- Within 1 business day of receipt of the eligibility check list, the RPCI Network QA Coordinator will fax or email the cohort assignment and dose level.
- An email must be sent by the site to confirm receipt of the cohort assignment and to provide the planned treatment start date.

Phase 2 Protocol Registration Instructions

The Subject Screening and Enrollment Log must be faxed or emailed ([contact]) to the Roswell Park CRS QA Network Office within 1 business day of the date the participant is consented. Once the Investigator has determined that eligibility has been met, complete the eligibility check list and fax or email it to the Roswell Park Network QA Coordinator at [contact].

4. STUDY DEVIATIONS

- If a deviation has occurred to eliminate hazard, this must be reported to the RPCI Network, site IRB and any other regulatory authority involved in the study.
- ALL study deviations will be recorded on the **Study Deviation Log**.
- Participants inadvertently enrolled with significant deviation(s) from the study-specified criteria will be removed from the study, at the discretion of the Principle Investigator.

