9.0 Design

This is an open-label, single arm, non-randomized, multi-center Phase Ib/II study of sorafenib when administered with pembrolizumab in patients with advanced hepatocellular carcinoma. The study will include an initial Phase Ib safety lead-in cohort of 6 patients.

Prior to starting on the combination therapy of sorafenib + pembrolizumab, patients will have completed initial treatment with sorafenib alone and must be stable on sorafenib (at least 200 mg BID for a minimum of 1 week) before the introduction of pembrolizumab. The sorafenib starting dose will be at the discretion of the treating physician based on clinical assessment of the patient.

All participants will sign an informed consent prior to any study-related tests. All participants will meet the inclusion and exclusion criteria summarized in Section 3.1 and 3.2.

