the first 3 weeks of combination therapy (a medication diary will be provided during this time to monitor participant compliance: see Appendix F). All toxicities will be assessed upon completion of the first 6 evaluable patients to see if any higher than anticipated occurrence of sorafenib toxicity is seen due to the addition of pembrolizumab.

The goal of the study is to evaluate efficacy of the combination therapy, therefore patients who are removed from the study prior to receiving the soraf+pembro combination treatment will be replaced. This includes replacing patients who do not tolerate sorafenib alone, as administered in the 1st 4 - 6 weeks of the treatment regimen. In addition, the following patients will be replaced:

- Patient withdraws consent
- Withdrawal from study due to toxicity,
- Withdrawal from study due to liver failure
- Patients who withdraw before the Week 12 (± 1 week) response assessment (for reasons other than progression)

Patients who withdraw due to disease progression prior to the Week 12 (± 1 week) response assessment of the combination therapy will not be replaced and will be counted as non-responders in the response rate calculations.

Patients who complete the 4-6 week initial treatment with sorafenib alone, and withdraw from the study after being treated with the combination therapy will not be replaced and will be counted as non-responders in the response rate calculations.

Patients will receive sorafenib + pembrolizumab until progression. If a patient discontinues either agent due to toxicity, they will still be able to stay on study until progression. Clinical benefit will be considered when making decision to stop therapy as radiographic reflection of true failure of this combination is still unknown.

Disease assessment (imaging) will be done every 6 weeks from the start of C1D1 combination therapy, with a confirmatory assessment no less than 6 weeks after an irPR or irCR or irPD. Therapy will be continued until the confirmatory scan, even if progression is noted on the Week 12 scan. After the 12-week scan disease assessment will be done every 9 weeks (± 1 week). Note: Timing for assessing ORR in patients on immunotherapies is not clear. Disease stability is the commonly seen response to sorafenib alone. Allowing continuation until the confirmatory scan at Week 18, even if progression is seen, allows us to assess the true response to this novel combination.

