19.3 Efficacy Analysis

The response rate will be estimated as the binomial proportion of responders among evaluable patients and supported by Jeffreys' 95% confidence interval.

Time to tumor progression (TTP) will be measured from the date of study enrollment to the first observation of progressive disease. Overall survival (OS) will be measured from the date of study enrollment to the time of death from any cause. These variables will be estimated using the Kaplan-Meier method. Statistics describing the time to event distributions will be obtained from Kaplan-Meier methods and Proportional Hazards models. Continuous variables will be summarized with commonly used statistics (mean, standard deviation, median, etc.), with subgroup associations tested using the Wilcoxon Rank Sum test. Categorical variables will be summarized in contingency tables, with associations of interest assessed using Fisher's Exact Test. Given the exploratory nature of this study, all p-values less than 0.05 will be deemed statistically significant. No adjustment will be made to the significance threshold to control for the effects of multiple testing on the overall Type I error rate.

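### Removal of ineligible patients is discretionary and undated with scans in view, and section 9.1 conflicts on whether a treated patient so removed is replaced or counted as a non-responder

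*Combined protocol and SAP*

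**What the plan says.** Appendix A, section 4 (Study Deviations): "Participants inadvertently enrolled with significant deviation(s) from the study-specified criteria will be removed from the study, at the discretion of the Principle Investigator". Section 3 of the same appendix states that "RPCI does not grant exceptions to eligibility criteria". No time limit is given, nothing restricts the decision to information available before treatment, and no analysis-set consequence is named.

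Section 9.0 describes the trial: "This is an open-label, single arm, non-randomized, multi-center Phase Ib/II study of sorafenib when administered with pembrolizumab". Section 9.1 sets the scans: "Disease assessment (imaging) will be done every 6 weeks from the start of C1D1 combination therapy". No blinded or independent response review is described.

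Section 9.1 has four rules on patients who leave:

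- Anyone removed before receiving the combination is replaced.
- A further list of replaced patients includes this entry: "Patients who withdraw before the Week 12 (± 1 week) response assessment (for reasons other than progression").
- Progression before Week 12 has its own rule, which opens "Patients who withdraw due to disease progression prior to the Week 12": such cases are not replaced and count as non-responders.
- Patients who finish the sorafenib lead-in and "withdraw from the study after being treated with the combination therapy will not be replaced and will be counted as non-responders".

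Section 19.3 defines the estimate: "The response rate will be estimated as the binomial proportion of responders among evaluable patients". The only definition of evaluable is in section 9.1 (more than 75% of prescribed sorafenib in the first 3 weeks of combination), and it does not mention eligibility. Section 19 defines no all-treated set.

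**The concern.** Take a patient who has started the combination, has had a Week 6 scan, and is then found to have breached an eligibility criterion. Whether that patient leaves the study is a choice, made by someone who can see the scan. If leaving also means being replaced, the same breach can keep a shrinking tumour among the 27 and take a growing one out. Nobody need intend this; it is enough that the scan colours a judgement about what counts as significant.

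At stake is the primary decision. Three responders in 27 is a failure and four is a success, so exchanging one non-responder for a responder can change the conclusion. The estimated ORR would also be biased upward.

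**Working it through.** **Inputs.** Null ORR 0.05, alternative 0.20, type I error limit 5%, power 80%, success at 4 or more of 27 evaluable (section 19.1). Background response rate of about 2–3% (section 19.0). Accrual of 41 for at most 27 evaluable, with 38 expected at the lead site (section 4.0). ORR window of 6 months from the start of combination (section 8.0).

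**Step 1: reproduce the design.** With X binomial (27, p):

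- Type I error = P(X ≥ 4 | 27, 0.05) = 0.0437.
- Power = P(X ≥ 4 | 27, 0.20) = 0.818.

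Both agree with the stated 5% and 80%.

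**Step 2: apply section 9.1 to the patient in question** (on combination, past Week 6, before Week 12, removed as ineligible).

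| Rule in section 9.1 | Does it fit? | Consequence |
|---|---|---|
| Removed before combination | No, combination has started | – |
| Leaves before Week 12, not for progression | Yes, if removal counts as withdrawal | Replaced |
| Leaves for progression before Week 12 | No, if ineligibility is the recorded reason | – |
| Leaves after receiving combination | Yes, if removal counts as withdrawal | Not replaced; non-responder |

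Two rules fit and give opposite answers. Neither names ineligibility. Both speak of patients who withdraw, whereas Appendix A speaks of removal.

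**Step 3: size under the replacement reading.** Suppose k patients who would never respond are removed and replaced while every responder is kept. The trial then succeeds whenever at least 4 of 27 + k treated patients respond, so

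type I error = P(X ≥ 4 | 27 + k, p0).

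This is an upper bound, because it assumes that every removed patient is truly an eventual non-responder. The documents do not give k, so a range is shown.

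| k | n = 27 + k | p0 = 0.05 | p0 = 0.03 | p0 = 0.02 |
|---|---|---|---|---|
| 0 | 27 | 0.0437 | 0.0082 | 0.0019 |
| 1 | 28 | 0.0491 | 0.0093 | 0.0022 |
| 2 | 29 | 0.0548 | 0.0106 | 0.0025 |
| 3 | 30 | 0.0608 | 0.0119 | 0.0029 |

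Check of the first increment: the result flips only if 3 of the original 27 respond and the replacement responds. That adds P(X = 3 | 27, 0.05) × 0.05 = 0.10676 × 0.05 = 0.00534, and 0.04374 + 0.00534 = 0.0491 to four decimals.

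**Step 4: size under the other reading.** If the removed patient stays as a non-responder, n remains 27 and the type I error remains 0.0437. It also remains 0.0437 if removal and replacement are unrelated to outcome.

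**Step 5: reach.** Appendix A is the multi-site appendix (section 6.0). Expected patients outside the lead site: 41 − 38 = 3. If only they are covered, k cannot be expected to exceed 3, and reaching 3 would need all of them to be ineligible eventual non-responders who are selectively removed.

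**The case against.** The strongest case against is that section 9.1 already closes the gap. Its paragraph on patients who leave after receiving the combination covers this patient on its plain words. Moreover, section 9.1 uses the language of removal with replacement only for patients who have not yet had the combination. On that reading nobody is swapped. This is a fair reading but not a settled one. If the later paragraph covered everyone who leaves after combination starts, the entry on leaving before Week 12 would add nothing, since earlier leavers are already replaced. Replacement before Week 12 and non-response afterwards would give both rules effect, but the text does not say that either.

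Other points that stand:

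- The rule may not govern lead-site patients. The opening of Appendix A was not in the text available here, so its scope should be checked there. If it does not reach them, no other passage found says what happens to lead-site patients discovered to be ineligible.
- A patient without response at Week 6 may still respond within 6 months, so early selection is imperfect.
- At a null of 2–3%, type I error stays below 5% even if all 41 − 27 = 14 spare places were used this way (0.0340 at 3%). The null actually tested, however, is 5%.
- There are controls: a signed eligibility checklist before enrolment, a deviation log, prompt notice of withdrawals with reasons, and annual data and safety monitoring. They limit outcome-driven removal without excluding it.

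Two stronger readings are tempting and should not be drawn. A reader might infer that removal from the study ends safety and survival follow-up. Section 1.3, section 12.1 and footnotes 5 to 7 of Appendix E provide survival follow-up for all patients, end-of-treatment evaluations and a safety visit, with no exemption for ineligible patients. Only response imaging lapses: Appendix E schedules no CT after the end-of-study visit. A reader might also take all 14 spare places at the 5% null and quote a type I error of 14.7%. Nothing suggests that many ineligible enrolments, and the spare places also serve the other replacement grounds.

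**Conclusion.** The concern holds as a gap and a contradiction, not as an established route to replacement. Appendix A permits a removal decision made with scan results in view, and section 9.1 does not settle how that patient enters the primary denominator.

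The effect is modest. At the 5% null, one selective replacement stays within the limit (at most 4.9%), while two or three exceed it (at most 5.5% and 6.1%). These figures rest on the replacement reading, on perfect selection of eventual non-responders, and on an assumed number of ineligible enrolments. Without the first two there is less inflation or none. The documents do not support a claim that such a patient will be replaced, or that bias is expected. They do leave the denominator of a 4-of-27 decision open to interpretation, which should be corrected.

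**What to change.** Amend Appendix A section 4 and section 9.1 together, and make the result apply to all sites:

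1. Reconcile the two section 9.1 rules for patients who leave after combination starts but before Week 12, and say which of them, if either, applies to removal for ineligibility.
2. State that ineligibility is judged on pre-treatment data only, without reference to on-study scans.
3. State that a patient found ineligible before the first pembrolizumab dose is replaced. One found ineligible after that dose stays in the primary ORR denominator and is not replaced on that ground. Response assessment continues where possible, and the existing safety and survival follow-up is kept.
4. In section 19.3, add ORR excluding ineligible patients as a sensitivity analysis.

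This concerns the analysis set and follow-up only. Whether and when study treatment stops is left to the protocol's clinical sections.

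Cost: amendment wording, with no added patients. The drawback is that a few ineligible patients may remain in the primary analysis, so ORR could be slightly lower; the sensitivity analysis shows by how much. As far as this route is concerned, type I error then stays at 4.4%.
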